6.5.1.1 Dose Reduction

Deviations to mandatory dose interruptions and/or reductions are not allowed. A maximum of two trametinib dose level reductions and three dose level reduction for dabrafenib are allowed. Steps for dose modifications for trametinib and dabrafenib are listed in [Table 6-3](#).

Table 6-3 Dose Modification steps for dabrafenib and trametinib

	Dabrafenib	Trametinib
Starting dose^a	150 mg BID	2 mg once daily
1st level dose reduction	100 mg BID	1.5 mg once daily
2nd level dose reduction	75 mg BID	1 mg once daily
3rd level dose reduction	50 mg BID	Not allowed

^a Dose modification should be based on the worst toxicity demonstrated at the last dose

A dose reduction below 50 mg BID for dabrafenib or below 1 mg QD for trametinib is not allowed. If a dose reduction below 50 mg BID for dabrafenib is required, dabrafenib will be permanently discontinued but these participants will be allowed to continue trametinib. If a dose reduction below 1.0 mg QD for trametinib is required, then trametinib will be permanently discontinued, but these participants will be allowed to continue dabrafenib.

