6.5.2.14 Mandatory dose modification and management guideline thromboembolic events

Advise patients to immediately seek medical care if they develop symptoms of deep vein thrombosis (DVT) or pulmonary embolism (PE), such as shortness of breath, chest pain, or arm or leg swelling. If any signs or symptoms of venous thromboembolism are present, the participant will undergo specific laboratory and medical imaging studies to confirm it. The medical imaging study or studies selected will depend on the anatomic site or organ of involvement (e.g., Doppler ultrasound, venography, ventilation perfusion lung scan, angiography, MRI). If the diagnosis is confirmed, appropriate medical care according to standard local clinical practice should be initiated immediately.

Permanently discontinue trametinib for life threatening PE. Withhold trametinib for uncomplicated venous thromboembolism for up to 3 weeks; if improved, trametinib may be resumed at a lower dose level.

6.5.2.15 Mandatory dose modification and management guideline for new malignancies suspected to be related to dabrafenib and/or trametinib treatment

[figure not shown]
New cutaneous malignancies:

Cutaneous squamous cell carcinoma (CuSCC), keratoacanthomas (KA) and new primary melanomas have been observed in participants treated with dabrafenib and dabrafenib/trametinib combination therapy. These treatment-related lesions should be surgically removed according to institutional practices. Dose modification or interruption of study treatment is not required for CuSCC, KA, or new primary melanoma, however CuSCC and new primary melanoma should be reported as a SAE. In addition, a biopsy of the lesion should be taken, where possible, and submitted for further analyses and a summary of the results submitted to Novartis.

Participants should be instructed to immediately inform their physician if new lesions develop. Skin examination should be performed prior to initiation of study treatment and throughout therapy as detailed in the Visit Evaluation Schedule. Monitoring should continue every month for 6 months following discontinuation of dabrafenib or until initiation of another anti-neoplastic therapy.

New non-cutaneous malignancies:

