In vitro experiments have demonstrated paradoxical activation of MAP-kinase signaling in *BRAF* wild type cells with RAS mutations when exposed to *BRAF* inhibitors, which may lead to increased risk of non-cutaneous malignancies in participants treated with dabrafenib. Cases of RAS-driven malignancies have been seen with *BRAF* inhibitors, including dabrafenib. Participants should be monitored as clinically appropriate. Consider the benefits and risks before continuing treatment with dabrafenib in participants with a non-cutaneous malignancy harboring a RAS mutation. No dose modification of trametinib is required when taken in combination with dabrafenib.

Following discontinuation of dabrafenib, monitoring for non-cutaneous secondary/recurrent malignancies should continue for up to 6 months or until initiation of another anti-neoplastic therapy.

New cutaneous and non-cutaneous malignancies that are reported to the Investigator should be reported as a SAE. A biopsy of the new malignancy should be taken, where possible, and submitted for further analyses including RAS mutation status. Testing of these biopsies may include analysis of genomic alterations, which include but not limited to DNA, RNA and protein analysis of these biopsy specimens, and would analyze the biological pathways known to be associated with, and relevant to, *BRAF*-mutant tumor activation.

6.5.2.16 Mandatory dose modifications and recommended clinical management guidelines for abnormal liver enzyme

Guidelines for dose modification and management of abnormal liver enzyme functions considered to be related to study treatment by the investigator are provided in [Table 6-16](#).

In addition to the instructions below, participants with normal baseline transaminases and bilirubin who experience sudden elevations even within Grade 1, should be monitored more closely.

Table 6-16 Mandatory dose modifications and recommended clinical management guidelines for abnormal liver enzyme test

Abnormal liver enzyme tests/hepatitis		
Grade	Recommended adverse event management guidelines	Mandatory dose modification requirements
Grade 2: AST or ALT >3× ULN to ≤ 5× ULN and/or bilirubin > 1.5× ULN to ≤ 3× ULN	
Monitor hepatic laboratory tests more frequently(every 2-3 days) until returned to baseline values	
Interrupt, dabrafenib and trametinib until ≤ Grade 1, and then reinstate, dabrafenib and trametinib at the same dose level.

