For participants who discontinue treatment for reasons other than documented disease progression as determined by investigator, death, lost to follow-up, or withdrawal of consent, tumor assessments must continue to be performed every 6 weeks until Week 36 and then every 12 weeks until documented disease progression as determined by investigator, death, lost to follow-up, or withdrawal of consent.

In some circumstances participants may be allowed to continue to receive study treatment beyond disease progression as per RECIST criteria as determined by investigator. These participants will continue assessments as outlined in the assessments section, and will complete the EOT visit only after permanent discontinuation of study treatment. After study treatment discontinuation, at a minimum, in abbreviated visits, the following data should be collected at clinic visits or via telephone/email contact (per assessment schedule in [Table 8-1](#))

- new / concomitant treatments including any radiotherapy, surgical procedure or new anticancer therapy
- adverse events/Serious Adverse Events
- survival status

Monthly safety follow up should continue for up to 6 months or until initiation of another anti-neoplastic therapy for monitoring for patients with cutaneous and non-cutaneous malignancies.

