9.2 Study completion and post-study treatment

Study completion is defined as when the last participant finishes their Study Completion visit and any repeat assessments associated with this visit have been documented and followed-up appropriately by the Investigator or, in the event of an early study termination decision, the date of that decision.

All treated participants should have a safety follow-up call conducted 30 days after last administration of study treatment. The information collected is kept as source documentation. All SAEs reported during this time period must be reported as described in [Section 10.1.3](#). Documentation of attempts to contact the participant should be recorded in the source documentation.

Following discontinuation of study treatment, all participants are to be followed as specified in [Section 9.1](#). The End of Study eCRF should only be completed when a participant is no longer being followed.

The primary analysis was conducted when the first 20 enrolled participants have had at least two post-baseline tumor assessments or have discontinued study earlier for any reason prior to the second post-baseline disease assessment. The primary analysis data will be summarized in

the primary clinical study report (CSR). Following the cut-off date for the analysis reported in the primary CSR, the study will remain open. Ongoing participants will continue to receive study treatment and be followed as per the schedule of assessments, as long as participants derive benefit from dabrafenib in combination with trametinib.

The study will end 17 months after the LPFV or when all participants have died or discontinued from the study, whatever occurs first.

At the end of the study, every effort will be made to continue provision of study treatment outside this study in alignment with local regulations through an alternative setting (e.g. another clinical study, Post Trial Access (PTA)) to participants who in the opinion of the Investigator are still deriving clinical benefit. The final analysis will occur at the end of the study. All available data from all participants up to this cut-off date will be analyzed and summarized in a final CSR.

10 Safety monitoring and reporting

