12.5.2 Safety endpoints

For all safety analyses, the FAS will be used.

Safety summaries (tables, figures) include only data from the on-treatment period with the exception of baseline data which will also be summarized where appropriate (e.g. change from baseline summaries). In addition, a separate summary for death including on treatment and post treatment deaths will be provided. In particular, summary tables for adverse events (AEs) will summarize only on-treatment events, with a start date during the on-treatment period (treatment-emergent AEs).

The on-treatment period lasts from the date of first administration of study treatment to 30 days after the date of the last actual administration of any study treatment.

The overall observation period will be divided into three mutually exclusive segments:

1. Pre-treatment period: from day of participant's informed consent to the day before first dose of study treatment
2. On-treatment period: from day of first dose of study treatment to 30 days after last dose of study treatment
3. Post-treatment period: starting at 31 day after last dose of study treatment.

Adverse events

The number (and percentage) of participants with treatment emergent adverse events (events started after the first dose of study treatment or events present prior to start of treatment but increased in severity based on preferred term) will be summarized in the following ways:

- by primary system organ class and preferred term.
- by primary system organ class, preferred term and severity (based on CTCAE v 4.03)

Separate summaries will be provided for study treatment related adverse events, death, serious adverse events, adverse events of special interest (AESI), other significant adverse events leading to dose adjustment and discontinuation.

The list of AESI's will also include relevant events for dabrafenib and trametinib which will be defined in the SAP.

A participant with multiple adverse events within a primary system organ class is only counted once towards the total of the primary system organ class.

Vital signs

All vital signs data will be listed by participant, and visit/time and if ranges are available, abnormalities (and relevant orthostatic changes) will be flagged. Summary statistics will be provided by treatment and visit/time.

12-lead ECG

1. PR, QRS, QT, QTcF, and RR intervals will be obtained from 12-lead ECGs for each participant during the study. ECG data will be read and interpreted (centrally/locally).

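### AESI tables stop 30 days after the last dose of any study drug, so a new malignancy recorded later, within the protocol's surveillance of up to 6 months after dabrafenib, is listed but not counted

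*Protocol*

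**What the plan says.** **Counting rule.** Protocol 12.5.2 (Safety endpoints) states that "summary tables for adverse events (AEs) will summarize only on-treatment events, with a start date during the on-treatment period (treatment-emergent AEs". The on-treatment period runs from first dose "to 30 days after the date of the last actual administration of any study treatment". SAP 2.1.1.6 uses the same boundary, with the post-treatment period starting on day 31. SAP 2.7.1 restricts AE summaries to on-treatment events and flags the others in the listings. The one stated exception is that "a separate summary for death including on treatment and post treatment deaths will be provided"; SAP 2.7.2 carries this through.

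**The AESI.** Protocol 12.5.2 requires an AESI summary. New primary or secondary malignancy is an AESI for dabrafenib (Protocol 10.1.1, SAP 2.7.1.1) and, in the SAP, also for the combination. Neither document gives AESIs a longer window.

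**Surveillance.** Protocol 6.5.2.15 says of cutaneous malignancies: "Monitoring should continue every month for 6 months following discontinuation of dabrafenib or until initiation of another anti-neoplastic therapy". Of the others it says that "monitoring for non-cutaneous secondary/recurrent malignancies should continue for up to 6 months or until initiation of another anti-neoplastic therapy". Protocol 9.1.1 adds a sentence on monthly safety follow-up for up to 6 months, worded for patients with cutaneous and non-cutaneous malignancies. It also lists "adverse events/Serious Adverse Events" among the data to collect after treatment stops, as scheduled in Table 8-1.

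**Two clocks.** Surveillance runs from the end of dabrafenib, while the table window runs from the last dose of either drug. The dates can differ: under Protocol 6.5.1.1, "dabrafenib will be permanently discontinued but these participants will be allowed to continue trametinib".

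**The concern.** For this one AESI the protocol looks for events over a longer period than its incidence table can count. A participant with a malignancy starting, say, three months after stopping both drugs could be in the listing while the AESI table shows none. A listing has no denominator, so a reader who takes the rate from the table would understate what was recorded.

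At stake is the description of a named safety event, within a secondary objective. The primary endpoint, response rate by central review, does not depend on it.

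**Working it through.** The plan states no figure to reproduce. The check is date arithmetic on the two windows, plus an exact interval to show what one case would do.

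**Inputs**
- Table tail: 30 days after the last dose of any study drug (Protocol 12.5.2, SAP 2.1.1.6).
- Surveillance: up to 6 months after dabrafenib, ending earlier at new anti-neoplastic therapy (Protocol 6.5.2.15).
- Study end: "The study will end 17 months after the LPFV or when all participants have died or discontinued from the study" (Protocol 9.2). LPFV is not in the abbreviation list. I assume it is the last participant's first visit, 0 to 28 days before first dose.
- Planned n: about 40.
- One month = 365.25/12 = 30.44 days, so 6 months = 182.6 days.

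**Formula.** Gap = max[0, min(last dabrafenib dose + 182.6, start of new therapy, study end) − (last dose of any study drug + 30)], in days.

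**Maximum.** Both drugs stop together, with no new therapy and full follow-up: 182.6 − 30 = 152.6 days. That is 152.6/182.6 = 84% of the surveillance period.

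**New therapy k months after both drugs stop** (k assumed), 30.44k − 30:
- k = 1: 0.4 days
- k = 2: 30.9 days
- k = 3: 61.3 days
- k = 4: 91.8 days
- within 30 days: none

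**Trametinib continued t days after dabrafenib** (t assumed), 152.6 − t:
- t = 30: 122.6 days
- t = 60: 92.6 days
- t = 90: 62.6 days
- t = 120: 32.6 days
- t ≥ 152.6: none

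**Study end, last participant, both drugs stopped together.** Time available from first dose is 17 months less 0 to 28 days, or 17.0 to 16.1 months. The full gap fits only if treatment stops by 17.0 − 6 = 11.0 months (10.1 at the lower bound). No gap remains if it stops after 17.0 months − 30 days = 16.0 months (15.1 at the lower bound). Earlier enrollees have more room.

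**Effect of one late case at n = 40** (the case is assumed; the documents give no malignancy rate). Clopper-Pearson 95% limits:
- 0/40: 0% (0 to 8.8%), upper limit 1 − 0.025^(1/40)
- 1/40: 2.5% (0.1 to 13.2%)

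**The case against.** **There is no contradiction, and a treatment-emergent table is a legitimate choice.** This stands. Protocol 12.5.2 and the SAP agree, a surveillance instruction does not promise a tabulation window, and late events have a prespecified place in a flagged listing. With about 40 participants, individual cases can be read there. This argues against changing the existing tables. It does not argue against one added summary for an event with its own post-treatment surveillance; deaths already get similar treatment.

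**Late events may already count.** Protocol 12.5.2 also describes treatment-emergent events in a parenthesis without an end date. The explicit on-treatment limit in the same section, repeated in SAP 2.7.1, governs the tables.

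**Late cases may not reach the database.** This stands and limits the point. Protocol 10.1.1 requires AE monitoring for at least 30 days. Protocol 10.1.3 sends later SAEs to the sponsor only if causality is suspected, whereas 6.5.2.15 asks for new malignancies to be reported as SAEs without a time limit. The 9.1.1 collection is tied to Table 8-1, which, as it reads here, marks AEs at end of treatment and end of study but not in the follow-up columns (column alignment is uncertain). The monthly sentence in 9.1.1 could also be read as covering only participants who already have a malignancy. A reader might infer that the listing keeps every late case; the documents support this only for cases entered on the AE page.

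**The size can be overstated.** Taking the global study's median PFS of 9.7 to 10.9 months as treatment length, a reader might conclude that 128 to 153 days remain even for the last participant. That borrows another study's PFS as exposure time, although treatment beyond progression is allowed, and assumes no new therapy after stopping. It is an upper bound only.

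**Conclusion.** The point holds as a mismatch between the AESI counting window and the malignancy surveillance period. A new malignancy that starts more than 30 days after the last dose of any study drug, and is recorded on the AE page, would be listed and flagged but left out of the tabulated incidence.

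The size is in days of coverage: at most about 153 of 183 per participant, assuming both drugs stop together, no new therapy and complete follow-up. A reader might infer that cases are being missed or that the AESI rate is biased by a known amount. The documents support neither, since they give no malignancy rate and the number of late cases may be zero. The improvement is worth making because it is cheap; no trial conclusion depends on it.

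**What to change.** Keep the treatment-emergent tables unchanged. Add to SAP 2.7.1.1 one supplementary summary of new primary/secondary malignancy in the Full Analysis Set, with two rows:

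1. On-treatment cases, with the same count as the treatment-emergent table.
2. Cases starting after the on-treatment period, up to 6 months after the last dabrafenib dose and before new anti-neoplastic therapy.

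Label row 2 as a crude minimum count of recorded cases. Do not present time to last contact as malignancy-monitored time: under SAP 2.1.1.5 and Protocol 9.1.2, last contact can be a survival phone call.

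Separately, reconcile Protocol 6.5.2.15, 9.1.1, 10.1.1 and 10.1.3 and Table 8-1 on how malignancies starting after day 30 are recorded.

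The cost is one more descriptive table built from dates the plan already uses (doses per drug, AE onset, subsequent therapy). Ascertainment after day 30 stays incomplete, and the reported figure may be slightly higher.

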12.5.3 Pharmacokinetics

Plasma concentration data of dabrafenib, dabrafenib metabolites (hydroxy-dabrafenib, and desmethyl-dabrafenib), and trametinib will be listed by participant, and visit/sampling time point. Descriptive summary statistics will be provided by visit/sampling time point. Summary statistics will include mean (arithmetic and geometric), SD, CV (arithmetic and geometric), median, minimum, and maximum. PAS will be used for pharmacokinetics.

12.5.4 Patient reported outcomes

Quality of life, as measured by the EORTC-QLQ C30, LC13 and the EQ-5D-5L, will be listed. Descriptive summaries and change from baseline will be provided, as appropriate.

12.7 Interim analyses

Not applicable.

[REDACTED]

[REDACTED]

[REDACTED]

[REDACTED]

13 Ethical considerations and administrative procedures

13.1 Regulatory and ethical compliance

This clinical study was designed and shall be implemented, executed and reported in accordance with the International Conference on Harmonisation (ICH) Harmonized Tripartite Guidelines for Good Clinical Practice, with applicable local regulations (including European Directive 2001/20/EC, US CFR 21), and with the ethical principles laid down in the Declaration of Helsinki.

13.2 Responsibilities of the investigator and IRB/IEC

Before initiating a trial, the investigator/institution must obtain approval/favorable opinion from the Institutional Review Board/Independent Ethics Committee (IRB/IEC) for the trial protocol, written informed consent form, consent form updates, participant recruitment procedures (e.g. advertisements) and any other written information to be provided to participants. Prior to study start, the investigator is required to sign a protocol signature page confirming his/her agreement to conduct the study in accordance with these documents and all of the instructions and procedures found in this protocol and to give access to all relevant data and records to Novartis monitors, auditors, Novartis Quality Assurance representatives, designated agents of Novartis, IRBs/IECs, and regulatory authorities as required. If an inspection of the clinical site is requested by a regulatory authority, the investigator must inform Novartis immediately that this request has been made.

13.3 Publication of study protocol and results

The protocol will be registered in a publicly accessible database such as clinicaltrials.gov and as required in EudraCT. In addition, after study completion (defined as last patient last visit) and finalization of the study report the results of this trial will be submitted for publication and posted in a publicly accessible database of clinical trial results, such as the Novartis clinical trial

[REDACTED]

results website and all required Health Authority websites (e.g. Clinicaltrials.gov, EudraCT etc.).

For details on the Novartis publication policy including authorship criteria, please refer to the Novartis publication policy training materials that were provided to you at the trial investigator meetings.

13.4 Quality Control and Quality Assurance

Novartis maintains a robust Quality Management System (QMS) that includes all activities involved in quality assurance and quality control, to ensure compliance with written Standard Operating Procedures as well as applicable global/local GCP regulations and ICH Guidelines.

Audits of investigator sites, vendors, and Novartis systems are performed by auditors, independent from those involved in conducting, monitoring or performing quality control of the clinical trial. The clinical audit process uses a knowledge/risk based approach.

Audits are conducted to assess GCP compliance with global and local regulatory requirements, protocols and internal SOPs, and are performed according to written Novartis processes.

14 Protocol adherence

This protocol defines the study objectives, the study procedures and the data to be collected on study participants. Additional assessments required to ensure safety of participants should be administered as deemed necessary on a case by case basis. Under no circumstances including incidental collection is an investigator allowed to collect additional data or conduct any additional procedures for any purpose involving any investigational drugs under the protocol, other than the purpose of the study. If despite this interdiction prohibition, data, information, observation would be incidentally collected, the investigator shall immediately disclose it to Novartis and not use it for any purpose other than the study, except for the appropriate monitoring on study participants.

[figure not shown]
Investigators ascertain they will apply due diligence to avoid protocol deviations. If an investigator feels a protocol deviation would improve the conduct of the study this must be considered a protocol amendment, and unless such an amendment is agreed upon by Novartis and approved by the IRB/IEC and Health Authorities, where required, it cannot be implemented.

